8.2.3.2 Change in post-bronchodilator spirometry test

Changes in the spirometry data at the different follow-up visits will be given and analyzed using the main measures of central tendency and dispersion (mean, median, standard deviation, confidence intervals, minimum, maximum and interquartile range).

- FEV1
- FVC
- FEV1/FVC

The study will examine whether there has been a significant change in the spirometry data over time, both in the total sample of evaluable patients and in each of the subpopulations established based on the severity of the COPD and type of patient, using the Student's t-test for paired data or its non-parametric equivalent, the Wilcoxon test. The % reduction in the parameters FEV1, FVC and FEV1/FVC will be calculated at the 24-month visit relative to baseline ((final value-baseline value)*100/baseline value).

The Student's t-test, one-way ANOVA or its non-parametric equivalents, the Mann-Mann U test or Kruskal-Wallis H test will be used in order to determine if statistically

significant differences in FEV1, FVC, FEV1/FVC (% reduction compared to the FEV1, FVC and FEV1/FVC baseline values) are observed, depending on the severity of the COPD and type of patient (exposed/unexposed).

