## **Study procedures**

Subjects identified with COPD will be informed about the study and invited to participate by investigators at the time of their routine control visits. All therapies will be prescribed according to the updated National COPD Guidelines (GesEPOC) indicating among other therapies active reduction of risk factors, influenza and pneumococcal vaccination (with PCV13) in all patients with mild, moderate or severe COPD. All the patients will be counselled to stop smoking and advised on life-style modifications. Any vaccination will be prescribed according to clinical practice and not related to the decision to include the subjects in the study. Subjects may be vaccinated before or after inclusion in the study.

Study will include periodic scheduled visits for all patients, to complete a total follow up of 2 years (see Table 1).

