**TABLE 1. FOLLOW UP VISITS**

	Visit	0	1	2	3	4	5
	Month	0	1	6	12	18	24
Verification of inclusion/exclusion criteria		X	X	X	X	X	X
Informed consent signature		X					
Demographic variables		X					
Exacerbations and smoking history		X	X	X	X	X	X
Clinical history (hospital and/or primary care)		X					
Performance or verification of recent spirometry		X			X		X
Completion of QOL test		X			X		X
Treatment and vaccination recommendations adjustment (as per normal clinical practice)		X			X		X
Telephone Follow up (if applicable)				X		X	
PCV13 vaccination record			X		X		X
Influenza vaccination record			X		X		X
Updated treatment record			X		X		X

**Definitions:**

- COPD exacerbations are defined as a complex of two or more respiratory symptoms (worsening dyspnea, cough, sputum production, chest tightness, or wheezing) related to the underlying COPD, with duration of 3 days or more, that require a change in treatment.
  - *Treatment changes* include acute treatment with antibiotics and/or steroids, or an addition of new maintenance bronchodilator.
  - *Mild exacerbations* are those that require new prescription of bronchodilator only
  - *Moderate exacerbations* are those that require antibiotics and/or systemic corticosteroids without hospitalization,
  - *Severe exacerbations* are those that lead to hospitalization.
- The onset date of exacerbations is defined by the onset of the first recorded symptom.
- Exacerbations that occur within 7 days of onset of a prior exacerbation are counted as a single exacerbation

A subject presenting with exacerbation, will be considered as vaccinated at least 15 days after receiving immunization

Redacted

- Immunosuppression:
  - Lymphoma/Leukemia
  - Another neoplasm subjected to immunosuppressing treatments
  - Organ transplant with its corresponding immunosuppressing treatment
  - Leukopenia<1.000/mm; neutropenia<500/mm
  - Patients infected by Human Immunodeficiency Virus (HIV)
  - Congenital immunodeficiency
  - Diseases that requires continuous treatment with systemic corticosteroids administration for more than 14 days (prednisone at doses> 15 mg/day or other equivalent preparations), or cytotoxic agents during the previous six months.

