## **8.7. Data analysis**

Depending on recruitment and data availability an interim analysis may be performed after the first year, if at least 75% of subjects included have completed one year of follow up.

- To determine the impact of PCV13 vaccination, the incidence of exacerbations will be determined 2 years after the inclusion in the study and will be compared with the incidence 2 years before the study (2 years of clinical history required including records of previous moderate/severe exacerbations, influenza and pneumococcal vaccination history comorbidities and previous treatments)
- A descriptive analysis of all variables will be performed. Qualitative variables will be analyzed by absolute and relative frequencies. Quantitative variables will be studied by the usual centralization and dispersion measures (mean, median, standard deviation, confidence intervals, minimum, maximum and interquartile range).
- For comparison of independent samples, the Pearson chi-squared test or the exact Fisher test for 2x2 tables or likelihood ratio for mXn tables, for qualitative variables, will be used. The Student's t test, one-way ANOVA or its non-parametric equivalent U-Mann-Mann, H-Kruskal-Wallis for quantitative variables will be used.
- For comparison of paired samples, the McNemar's test will be used for qualitative variables and Student's t test or Wilcoxon's test for quantitative variables.
- A multivariate logistic regression analysis will be performed, in order to identify risk factors associated with exacerbations. Exacerbations existence (yes/no) will be used as dependent variable. Vaccination with PCV13 and statistically significant variables in the univariate model, will be used as possible risk factors: demographic characteristics, influenza vaccination, smoking habit, etc. In addition, potential confounding variables will be considered: phenotype, comorbidities, COPD severity, FEV1 (no control possible based on the study design)
- Appropriate tests will be performed accordingly to determine if the necessary requirements are fulfilled for the use of parametric contrasts.
- Estimates will be performed with a 95% confidence interval. The SPSS statistical package version 19.0 or later will be used.

Redacted

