The change in the quality of life of the patients according to the Saint George's questionnaire will be studied, presenting the main measures of central tendency and dispersion (mean, standard deviation, median, minimum, maximum, IR and 95%CI), both for the total score obtained and for the three domains of Symptoms, Activity and Impacts. We will explore whether there are statistically significant differences in the quality of life of patients depending on the severity of COPD and the type of patient using the Student's t-test or its non-parametric equivalent Mann-Whitney U test, depending on the distribution of the variables.

We will examine whether there has been a significant change over time in quality of life, both for the total sample of evaluable patients and in each of the subpopulations established based on the severity of COPD and the type of patient, using the paired Student's t-test or its non-parametric equivalent, the Wilcoxon test.

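### SAP 8.2.3.2 compares baseline-to-month-24 spirometry change by ever/never PCV13 without using the vaccination date, and SAP 8.2.3.7 gives quality of life no vaccination anchor either

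*SAP*

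**What the plan says.** **Spirometry.** SAP 8.2.3.2: "The % reduction in the parameters FEV1, FVC and FEV1/FVC will be calculated at the 24-month visit relative to baseline". The same section then tests whether this percentage differs between exposed and unexposed patients.

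**Exposure.** SAP 5.4 and 8.2.1 define the two groups only by whether the patient received PCV13. They set no cut-off date and no minimum time since the dose. The protocol's 15-day rule (definitions under Table 1) is written for exacerbations only.

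**Timing of the vaccine.** Protocol 8.2, Study procedures: "Subjects may be vaccinated before or after inclusion in the study". Table 1 schedules the item "PCV13 vaccination record" at months 1, 12 and 24, and revisits vaccination recommendations at months 0, 12 and 24.

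**Timing of the assessments.** In Table 1, "Performance or verification of recent spirometry" and "Completion of QOL test" both fall at months 0, 12 and 24. Baseline spirometry may be up to 6 months old, or be done around visit 1, give or take a month (protocol 8.2.1; SAP 5.1.1).

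**Quality of life.** SAP 8.2.3.7.1: "We will examine whether there has been a significant change over time in quality of life", by paired tests, with a separate comparison of quality of life between groups. SAP 8.2.3.7.2 has parallel wording for the CAT. Neither names the visits compared or refers to the vaccination date.

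**Elsewhere in the SAP.** Among vaccinated patients, time is split at the PCV13 date for exacerbations (8.2.3.1) and for costs (8.2.3.6).

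**The concern.** Secondary objectives 2 and 3 ask what PCV13 does to quality of life and to FEV1 decline. That requires knowing which part of each patient's record lies after the vaccine. The spirometry window is tied to study visits, while exposure can begin at any point before or inside that window. Two distortions follow:

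- **Vaccinated before inclusion.** The starting value will usually be post-vaccine. A one-off gain at vaccination has already happened and cannot appear as change. An ongoing effect on the rate of FEV1 decline would still be seen.
- **Vaccinated during follow-up.** The patient counts as exposed for the full 24 months, although part or all of the measured change came before the dose.

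There is also room for reverse causation. If patients who are declining are more likely to be vaccinated later, their pre-vaccine decline is booked to the vaccinated group. The result would be hard to interpret for either objective.

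**Working it through.** **Plan's own figure.** There is none to reproduce. The study-size sections (protocol 8.5, SAP 5) cover exacerbations only. No effect size, SD or power is given for FEV1 or quality of life.

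**Step 1: share of the window after the dose.** For PCV13 given t months after inclusion (0 to 24), taking the window as months 0 to 24:

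post-vaccine share = (24 − t) / 24

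| Dose at month | Calculation | Post-vaccine share |
|---|---|---|
| 0 | 24/24 | 100% |
| 1 | 23/24 | 96% |
| 6 | 18/24 | 75% |
| 12 | 12/24 | 50% |
| 18 | 6/24 | 25% |
| 24 | 0/24 | 0% |

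All of these patients enter SAP 8.2.3.2 as fully exposed.

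**Step 2: group-level range (assumed).** The documents give no vaccination dates. For illustration, let a share b of the exposed be vaccinated before inclusion and the rest evenly over months 0 to 24, whose mean post-vaccine share is 0.5.

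- Constant effect on FEV1 slope, share retained = b × 1 + (1 − b) × 0.5
- One-off level effect arising at the dose (for example on quality of life), share retained in a visit 0 to month 24 change = 1 − b

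| b | Slope effect retained | Level effect retained |
|---|---|---|
| 0% | 50% | 100% |
| 25% | 62.5% | 75% |
| 50% | 75% | 50% |
| 75% | 87.5% | 25% |

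The two endpoint types suffer in opposite circumstances, and no row leaves both intact. If instead every dose fell within months 0 to 1, at least 96% of the window would be post-vaccine and the problem would almost vanish. The level-effect column applies to quality of life only if the change is taken from visit 0 to month 24, which the SAP does not say.

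**Step 3: the baseline itself is loosely dated.** With spirometry up to 6 months old, the interval to month 24 can reach 24 + 6 = 30 months. With spirometry at month 1 plus one month, it can shrink to 24 − 2 = 22 months. In the second case the baseline can follow a dose given between visits 0 and 1. In the first, an older test can precede a dose given shortly before inclusion. Visit labels therefore do not settle whether a value is pre- or post-vaccine; only test dates do.

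**Step 4: would limiting the exposed group to doses between visits 0 and 1 work?** If doses were even over 24 months, 540 × 1/24 = 22.5 (about 22) of the planned 540 would qualify, or 264 × 1/24 = 11 of the 264 expected at two years. If only one third were spread evenly and the rest vaccinated by visit 0, it would be 540 × 1/3 × 1/24 = 7.5 of 540, unless some of those earlier doses were given on the visit day. That could nearly empty the main contrast.

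**The case against.** The best defence is that doses may cluster near inclusion. Guideline-based recommendation takes place at visit 0 and PCV13 is recorded at month 1, so many first doses could fall where 96% or more of the window is post-vaccine. That is plausible, and it means a reader should not infer that the baseline is commonly post-vaccine or that most of the credited change is pre-vaccine; nothing in the documents supports either. But the plan neither requires nor checks such clustering.

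Other stronger readings also fail:

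- **A fixed inclusion-to-month-24 change for SGRQ and CAT.** This window is written for spirometry only. For quality of life the defect is that no time points and no anchor are stated.
- **Vaccination as late as month 24 as a stated rule.** It follows only from the month-24 record and the missing cut-off; that record may simply capture doses since month 12.
- **Bias always toward zero.** Dilution works that way for a slope effect in patients vaccinated during follow-up. It does not apply to a slope effect in those vaccinated before inclusion, and reverse causation could push either way.
- **The same error in the exacerbation analysis.** Protocol 8.7 does count from inclusion ("the incidence of exacerbations will be determined 2 years after the inclusion in the study and will be compared with the incidence" over the 2 years before), but the SAP's paired pre/post comparison already runs from the PCV13 date, and 8.7 allows the SAP to modify the plan. The two texts should be reconciled; nothing more follows here.

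**Conclusion.** The point holds for spirometry as written, and for quality of life as a missing specification. Following SAP 8.2.3.2 literally credits pre-vaccine change to PCV13 in any patient vaccinated during follow-up, and uses a baseline that is usually post-vaccine in any patient vaccinated earlier. For one patient, the post-vaccine share of the window runs from 100% (dose at or before inclusion) through 50% (month 12) to 25% (month 18), and lower for later doses.

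For the study as a whole the size is unknown. The 50% to 87.5% (slope) and 25% to 100% (level) ranges rest on assumed vaccination dates, and near-complete clustering at months 0 to 1 would leave little bias. The direction is not assured. Only secondary objectives 2 and 3 are affected, so this should be corrected but does not threaten the primary analysis.

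**What to change.** In SAP 8.2.3.2 and 8.2.3.7:

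1. Classify exposure by PCV13 date, as the pre/post comparisons of exacerbations and costs already do.
2. Take as baseline the last value dated before PCV13, rather than relying on the visit label.
3. Treat exposure as time-varying across the month 0, 12 and 24 assessments: intervals that end before vaccination count as unexposed. State how an interval containing the dose is handled, since a patient vaccinated between the month 0 and month 12 assessments has no complete pre-vaccine interval.
4. Report patients vaccinated before inclusion as a separate group, usable for annualised FEV1 decline but not for a one-off change in quality of life.
5. Express FEV1 decline per year from actual test dates.
6. Name the time points for SGRQ and CAT.
7. Do not restrict the main exposed group to doses between visits 0 and 1; show that only as a sensitivity analysis if numbers allow.

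Separately, reconcile the time origin in protocol 8.7 with the SAP.

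**Cost.** SAP wording and slightly more analysis work. Vaccination dates are already needed for the exacerbation indices, so no new data are required. The price is smaller groups for two secondary objectives.

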### **8.2.1. Inclusion criteria**

Patients must meet all of the following inclusion criteria to be eligible for inclusion in the study:

1. Patient  $\geq 18$  years diagnosed with COPD (any stage, the subgroups for the analysis would be based on COPD severity grade)

Redacted

2. Evidence of a personally signed and dated informed consent document indicating that the patient (or a legally acceptable representative) has been informed of all pertinent aspects of the study.
3. Ability to understand and complete the required QoL questionnaires
4. At least 2 years of clinical history available that includes records of previous moderate/severe exacerbations, influenza and pneumococcal vaccination history comorbidities and previous treatments.
5. Spirometry data\* (maximum 6 months old, or if not available at enrollment, to be performed as per normal clinical practice at visit 1 +/- one month)

\*Subjects with FEV1 <40 should be less than 20% of the total study population (related to the microbiological etiology dependent on severity)

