### **8.3. Variables**

**Variables to be recorded from previous clinical history and follow up visits (according to Table 1):**

- Consent date
- Subject code
- Demographic and epidemiological data;
- Antropometric data (weight, height, body mass index (BMI), Waist Circumference)
- Smoking habit, alcohol consumption
- Spirometric data (FEV1, FVC, FEV1/FVC)
- Pharmacological treatment
- COPD severity (GOLD)
  - o GRADE 1: Mild/unknown [FEV1≤ 80%, FEV1/FVC < 0,7 or no spirometry data]
  - o GRADE 2: Moderate [50% ≤ FEV1< 80%,FEV1/FVC < 0,7]
  - o GRADE 3: Severe [30% ≤ FEV1 < 50%, FEV1/FVC < 0,7]
  - o GRADE 4: Very severe [FEV1< 30% o FEV1< 50% plus respiratory failure,FEV1/FVC < 0,7]
- Number and severity of exacerbations

Redacted

- Frequency of total exacerbations (moderate and severe) in the previous year and during follow-up (recorded at hospital or primary care level).
- Comorbidities
  - o high blood pressure
  - o dyslipidemia
  - o type 2 diabetes mellitus
  - o metabolic syndrome
  - o heart failure
  - o ischemic heart disease
  - o chronic kidney disease
  - o cirrhosis
- History of neoplasia (solid organ and hematologic)
- Pneumococcal vaccination
- Influenza vaccination
- QoL questionnaire (reduced SGRQ, CAT) - completed by subjects and transcribed into electronic case report form (CRF)

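### FEV1 change is tested across GOLD grades that are themselves cut on FEV1, so regression to the mean can produce a spurious severity difference whose net direction cannot be predicted

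*SAP*

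**What the plan says.** The outcome is defined in SAP 8.2.3.2: "The % reduction in the parameters FEV1, FVC and FEV1/FVC will be calculated at the 24-month visit relative to baseline", with the difference divided by the baseline value. For the group comparison, "The Student's t-test, one-way ANOVA or its non-parametric equivalents, the Mann-Mann U test or Kruskal-Wallis H test will be used" to see whether "differences in FEV1, FVC, FEV1/FVC (% reduction compared to the FEV1, FVC and FEV1/FVC baseline values) are observed, depending on the severity of the COPD" and, separately, on exposure. The same section looks for change over time "in each of the subpopulations established based on the severity of the COPD and type of patient, using the Student's t-test for paired data" or the Wilcoxon test. It names no baseline adjustment and does not mention regression to the mean.

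Severity is the GOLD grade, with FEV1 cut-points at 80, 50 and 30. Protocol 8.3 gives, for example, "GRADE 3: Severe [30% ≤ FEV1 < 50%, FEV1/FVC < 0,7". Entry needs one spirometry: "maximum 6 months old, or if not available at enrollment, to be performed as per normal clinical practice at visit 1" (Protocol 8.2.1). In Protocol Table 1 the row "Performance or verification of recent spirometry" is marked at months 0, 12 and 24 only. Neither document says which spirometry fixes the grade used for analysis.

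**The concern.** If one reading both assigns the grade and is the baseline of the change score, its measurement error enters twice. A reading that is low by chance moves a patient into a worse grade and also makes the later value look like a recovery. A reading that is high by chance does the reverse. The middle grades receive misplaced patients at both edges, so the errors partly offset. Grade 1 receives them only from below and Grade 4 only from above, so the errors do not offset there. The across-grade test can then reject when decline is the same in every grade, and the within-grade paired tests are shifted in the same way.

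At stake is a table of FEV1 change by severity that could report a statistically significant pattern with no clinical basis. It would appear in a study that also asks which severity group benefits most from vaccination.

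**Working it through.** **Inputs from the documents.** SAP section 5 gives 540 and 1000 enrolled, with 70% retention in each of two years: 540 × 0.7 × 0.7 = 264.6 and 1000 × 0.7 × 0.7 = 490. This reproduces the plan's 264 and 490, so N = 754 at month 24. The significance level is 0.05 (SAP section 4). Patients with FEV1 below 40 are to be under 20% of the study population (SAP 5.1.1). The plan states no SD, effect size or power for FEV1 change.

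**Assumptions, not in the documents.** True FEV1 has mean 55 or 60 and SD 17 % predicted, which stays within the 20% cap. True decline over two years is 4% in every grade. Measurement error is proportional, with CV 3%, 5% or 8%. Individual true change either does not vary or has an SD of about 4 or 8 percentage points.

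**One patient at a cut-point.** Take a true baseline of 50 and a true month-24 value of 50 × 0.96 = 48, with CV 5%.
- Baseline read one SD low: 47.5, so Grade 3. Apparent change is (48 − 47.5)/47.5 = +1.1%.
- Baseline read one SD high: 52.5, so Grade 2. Apparent change is (48 − 52.5)/52.5 = −8.6%.

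The true change is −4% in both cases.

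**False-positive rate of the across-grade ANOVA on % change (simulation, N = 754, equal relative decline).**

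| SD of individual change | Value that sets the grade | CV 3% | CV 5% | CV 8% |
|---|---|---|---|---|
| none | baseline | 31–34% | 70–77% | 98–99% |
| 4 points | baseline | 17% | 56% | 98% |
| 8 points | baseline | 10% | 37% | 89% |
| 4 points | a separate test | 5% | 5% | 5% |
| 8 points | a separate test | 5% | 4% | 5% |

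The ranges in the first row come from repeated runs at means 55 and 60. Kruskal-Wallis is within about 2 percentage points of ANOVA in these proportional-error runs. With no measurement error the rate is 3–4%. With N = 400 and an 8-point SD it is 18% at CV 5% and 60% at CV 8%. The last two rows show the cause: once the grading value is separate from the change score, the excess disappears.

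**Scale of decline.** The planned metric divides by baseline, so *equal decline* must be tied to a scale. An equal absolute loss of 2.2 points is 2.2/80 = 2.8% at FEV1 80, 2.2/50 = 4.4% at 50 and 2.2/30 = 7.3% at 30. That gradient runs opposite to regression to the mean. The table shows mean apparent % change by grade, with grade set by the baseline value. Equal absolute loss is 60 mL with an individual SD of 120 mL and predicted FEV1 averaging 2.8 L. Equal relative decline uses the 8-point SD.

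| Truth | CV | Grade 1 | Grade 2 | Grade 3 | Grade 4 | ANOVA rejects |
|---|---|---|---|---|---|---|
| equal relative | 0% | −3.7 | −3.7 | −3.7 | −3.6 | 4% |
| equal relative | 5% | −5.5 | −3.6 | −2.8 | −2.4 | 37% |
| equal relative | 8% | −7.9 | −3.6 | −1.4 | −0.4 | 89% |
| equal absolute | 0% | −2.5 | −3.6 | −5.4 | −8.8 | 89% |
| equal absolute | 5% | −4.4 | −3.6 | −4.5 | −7.6 | 45% |
| equal absolute | 8% | −6.9 | −3.5 | −3.0 | −5.5 | 41% |

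**Does a later window repair it?** With grade fixed at baseline and month-12 to month-24 change, rejection is 5–6% for % change under proportional error and equal relative decline. It is 5% for absolute change under additive error and equal absolute decline. On the % scale it is not repaired in general. With additive error and equal relative decline, ANOVA still rejects about 24–45% of the time, partly through unequal variances (Kruskal-Wallis about 8–11%). With equal absolute loss, ANOVA rejects 26–100% of the time.

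**The case against.** **The grading visit is inferred.** No sentence ties the grade to the baseline reading, and Protocol 8.3 lists severity among variables taken from history and follow-up visits. Grade 4 can also depend on respiratory failure. This stands as a limit on certainty. It does not rescue the test: entry calls for one spirometry, the next is at month 12, and the grades are set out as analysis groups under patient disposition (SAP 8.2.1). Grading on the month-24 value instead gave 96–100% rejection at CV 3–8%, with the bias reversed (assumed 5-point SD of individual change).

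**Every variability figure is assumed.** This also stands. At CV 3% with wide individual variation the excess is modest, about 10% against 5%. A reader might infer that the study will very likely report the mildest patients declining most. The documents do not support that: it needs a within-patient variability they do not give, and equal relative rather than equal absolute loss.

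**The comparison answers no listed objective.** Secondary objective 3 concerns the effect of PCV13 on FEV1 decline, and its overall exposed/unexposed comparison is not cut on FEV1. Primary objective 2 is analysed through exacerbation rates (SAP 8.2.3.1). A reader might infer that either is biased by this mechanism, or that the SAP plans a paired FEV1 test in vaccinated patients by grade. Neither follows: SAP 8.2.3.2 treats severity and exposure as separate groupings and specifies no cross of the two.

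**Conclusion.** The point holds as a defect of the across-grade FEV1 test and the within-grade paired tests in SAP 8.2.3.2. If grade is set by the baseline reading, regression to the mean exaggerates decline in the mildest grade and masks it in the severest. With N = 754, proportional CV 3–8% and equal relative decline, the false-positive rate is about 10% to 99%, depending mainly on test-to-test CV and on how much true decline varies between patients. The percentage denominator can pull the other way, so a significant result in either direction could not be read as a real difference in decline, and its sign cannot be foretold. The consequence is a misleading secondary table; the mechanism does not reach the vaccine comparison of FEV1 overall or the exacerbation results.

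**What to change.** In SAP 8.2.3.2:

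1. Remove the across-grade significance test on baseline-to-month-24 change. Report by-grade changes and within-grade paired changes as descriptive only, with a note that they are subject to regression to the mean.
2. State that grade is fixed at the baseline spirometry.
3. If severity-specific FEV1 results are wanted, compare exposed with unexposed within baseline grade, adjusting for baseline FEV1 because exposure is not randomised. With equal FEV1 distributions the unadjusted within-grade test held 4–6%. With assumed cohort means of 52 and 62 it rose to 8–9% at CV 5% and 9–13% at CV 8%. Adjustment for an error-prone baseline does not remove regression towards different cohort means. The residue is about (1 − reliability) × difference in means. With SD 17 and an error SD of 3 points, reliability is 289/(289 + 9) = 0.97, leaving about 0.03 × 10 = 0.3 points. Report an estimate with its interval and state this limit.
4. If decline is still compared across grades, use month-12 to month-24 change with baseline grade, on a prespecified absolute or log-ratio scale, with a method that allows unequal variances (Welch ANOVA, for example).

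The cost is SAP wording and minor programming, since month-12 spirometry is already scheduled. The loss is real but small: there is no formal test of 24-month decline by grade, and any across-grade comparison covers 12 months and needs both later spirometries.
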